### **Study Coordinators:**

- [name], M.S. B.Eng., Assistant Research Engineer
- [name], B.S., Research Assistant II

**Population:** 20 patients, age: 18-60

**Number of Sites:** 1

**Study Duration:** 2 years

**Subject Duration:** 2-3 weeks

### **General Information**

Major depressive disorder (MDD) is one of the most disabling mental illnesses worldwide with a lifetime prevalence of about 17% in the United States [1, 2] and is associated with increased mortality [3, 4]. Treatment resistant depression (TRD), defined as reduced clinical response to adequate doses and duration of antidepressants, is a severe, chronic and most disabling form of MDD [5, 6]. The introduction of antidepressants revolutionized the field of mood disorders since 1950's. Antidepressants significantly reduced the morbidity, hospitalization and overall mortality of patients suffering from depression [7]. Despite this impressive progress, nearly 50% of depressed patients do not, unfortunately, fully respond to treatment [6, 8] and current antidepressants takes few weeks to work. Furthermore, there are no reliable clinical biomarkers available to predict who will respond to antidepressant treatment and thus patients often go through several trial-and-error attempts of different treatment strategies with only modest benefits. Identifying novel therapeutic targets for TRD is a critical priority as prolonged illness is a strong predictor of poor functional outcome [6, 9]. Consequently, there are two primary challenges in antidepressant research: (a) developing rapidly acting, safe and effective antidepressant treatments, and (b) developing noninvasive clinically useful biomarkers of antidepressant response with a focus on early indicators of treatment response. The serendipitous discovery of rapid and protracted antidepressant effect of Ketamine, a widely used anesthetic drug, has opened up development of novel glutamate based antidepressant treatment strategies. The overarching objective of the current project is to address the challenge of **developing biomarkers of Ketamine and its rapid antidepressant effect** through the use of well-validated, reliable and non-invasive clinical neurophysiological techniques such as electroencephalography (EEG) and transcranial magnetic stimulation (TMS).

### **Background Information**

Ketamine hydrochloride (HCl) is widely used anesthetic agent with intravenous bolus injection at of 1 to 4.5 mg/kg at a rate of 0.5 mg/kg/min can rapidly induce anesthesia starting within 30 seconds and lasting for 5–10 min [10]. The sub-anesthetic dose (0.5 mg/kg over 40 minutes) of Ketamine improves depression symptoms in patients with TRD [11-13], bipolar depression [14] and post-traumatic stress disorder [15] and also in reducing suicidal ideation (SI) in depressed patients [16, 17]. The improvement in depression scores were seen as early as 2 hours and the antidepressant effects persisted in up to 35% of patient at the end of 7 days [11]. Murrough et al 2013 [12] conducted a relatively larger (N=67 TRD), two site, randomized, parallel design clinical trial and confirmed the superior efficacy of Ketamine even compared to active placebo anesthetic drug, midazolam in reducing depression symptoms. ]The response rates to Ketamine vs. midazolam were 64% and 28%, respectively with strong effect size (Cohen's d 0.7) and 21 out of 47 patients Ketamine-treated patients continued to exhibit improved scores over the 7-day period and thus highlighting inter-individual variability in duration of response to Ketamine. A subsequent study found that **early antidepressant response to the first infusion**

**was highly predictive of a sustained response to subsequent infusions** [18]. Thus, even though the efficacy of ketamine has been clearly established by many studies, the exact underlying neural mechanisms involved in Ketamine's rapid antidepressant effect is still unclear [23]. Ketamine is a n-methyl aspartate (NMDA) antagonist and administration at low doses transiently increases glutamate release in the frontal cortex, thus enhancing glutamatergic neurotransmission presumably through non-NMDA mechanisms such as  $\alpha$ -amino-3-hydroxy-5-methyl-4-isoxazole propionic acid (AMPA), metabotropic glutamate, and kainate receptors [24, 25]. Indeed, AMPA antagonist pretreatment abolishes Ketamine's antidepressant effect [26]. Anesthetic dose of Ketamine is however not associated with glutamate release [25]. NMDA receptor antagonism decreases the activity of cortical parvalbumin-positive interneurons and causes cortical excitation by disinhibition of pyramidal neurons [25]. Recent neurobiological studies suggest that Ketamine induced NMDA blockade triggers a complex intracellular cascade - Ketamine upregulates BDNF expression by inhibiting eukaryotic elongation factor (eEF2) kinase [27], and increases synaptic protein synthesis and spine formation in the prefrontal cortex (PFC) [28]. In summary, a sub-anesthetic dose of Ketamine induces increased glutamate activity and initiates synaptic plasticity processes presumably mediating the antidepressant effects [29, 30]. The challenge is to be able to validate these preclinical findings in patients with depression. In addition, it is unclear if the early increases in glutamatergic neurotransmission are related to the antidepressant action. If there are **non-invasive biomarkers** available, then it is possible to directly test in TRD patients if the **early antidepressant effect of Ketamine is related to enhanced glutamate neurotransmission and synaptic plasticity**.

#### Clinical markers of glutamate neurotransmission and synaptic plasticity

Substantial evidence has shown abnormalities in glutamatergic neurotransmission causing impairments in neural plasticity in mood disorders [31]. Magnetic resonance spectroscopy (MRS) has been employed to measure brain glutamate and glutamine. MRS Ketamine studies in healthy subjects have been inconsistent, showing no change or increased glutamate or glutamine. One study in TRD patients found Ketamine pretreatment low Glx/glutamate ratio (as a marker of glutamine) in the prefrontal cortex was associated with greater improvement [32]. Proton MRS measurements of glutamate and glutamine, especially at low field MRI, has poor spatial and chemical resolution. A  $^1\text{H}$ - $^{13}\text{C}$ -MRS at high MRI field show sub-anesthetic Ketamine dose increase glutamate/glutamine cycle in rats [33] but these findings require confirmation in human clinical subjects. **Peripheral BDNF levels:** Antidepressant treatment increases brain BDNF expression. While it is currently not possible to measure brain BDNF in patient, peripheral BDNF levels are decreased in patients with MDD [34] and serum BDNF increases is associated with antidepressant treatment response [35]. Ketamine significantly increased plasma Brain Derived Neurotrophic Factor (BDNF) levels in treatment responders compared to non-responders at 4 hours post-infusion [36, 37] and negatively correlated with the depression scores [38]. These results suggest that plasma BDNF at 4 hours post-infusion could be markers of Ketamine treatment response. However it is not clear if the BDNF increase is related to enhanced glutamate neurotransmission or synaptic potentiation.

#### Biomarker of prognosis and response to ketamine treatment

There is an urgent need of a biomarker of prognosis and response to treatment in patients with MDD. Pharmacogenetic studies have been trying to use genetic variants to predict the response to specific medications in patients, but most of the studies are still underpowered and the high genetic heterogeneity of the MDD population is hindering replication of most findings (Fabbri and Serretti, 2015). Specifically, associations with genetic variants are especially complicated because they require very large sample sizes and not often look into the functionality of those variants. In this context, switching the focus to functional genetic markers, such as DNA methylation and gene expression levels, to predict a priori the response to treatment, would overcome those limitations and allow for a more accurate and dynamic measure of how the cells of a given patient will actually respond to potential medications. This approach has been proposed by a recent study showing that the ex vivo cellular response to medications can predict the clinical outcome of the treatment in vivo. Specifically, the degree to which paroxetine reduced the phosphorylation of the enzyme DNA methyltransferase (thereby reducing its activity and increasing the expression of neurotrophic genes) in peripheral blood mononuclear cells of depressed patients significantly correlated with the reduction of depressive symptoms after six weeks of treatment (Gassen & Fries et al., 2015). In other words, the failure to improve symptoms was detected after seventy two hours of ex vivo treatment in blood cells. In this sense, the study aims to observe specific expression and/or methylation

markers measured in blood cells isolated treated ex vivo with a single dose of ketamine and its correlation with the clinical response to treatment in patients with treatment-resistant depression.

### Transcranial magnetic stimulation (TMS) measures of Cortical Excitability

TMS is a widely employed non-invasive brain stimulation (NIBS) technique to characterize neurophysiological function underlying neuropsychiatric illnesses [39], including markers of cortical excitability and plasticity that can elucidate the neurobiology of drug action [40]. TMS paradigms include measurements of motor evoked potentials (MEP) with surface electromyography (EMG) applied to hand muscles such as the abductor pollicis brevis (APB) after applying single or paired TMS pulses on the motor cortex [41, 42]. The motor cortex is an extensively studied target area for neurophysiological studies because changes in motor activation and excitability can be readily and reliably assessed by MEP [42]. **MEP amplitude, cortico-motor threshold (MT) and intra-cortical facilitation (ICF)** are commonly reported measures of cortical excitability function [42]. The MEP amplitude is measured as the average response to a series of TMS pulses applied at a consistent TMS intensity [43]. MEP amplitude is thought to be dependent on NMDA and voltage gated channels and thus modulated by NMDA and GABAergic drugs and a reliable measure of the excitatory/inhibitory balance of cortical pyramidal cells [39]. MT is a measure of corticospinal excitability and depends on the excitability of axons and that of synaptic connections at corticospinal level [40, 42]. Voltage-gated sodium (Na) channels regulate axon excitability and NMDA regulates fast excitatory synaptic neurotransmission in the neocortex [39]. Anticonvulsants with Na channel blocking properties increase MT. Ketamine, a NMDA antagonist, paradoxically decreases MT [44]. ICF assessments by TMS involve pairing a subthreshold (80% of RMT) conditioning stimulus followed by a suprathreshold test stimulus, with an interstimulus interval of 10–20 ms [39, 45]; such pre-conditioning facilitates (i.e. increases amplitude) the MEP. ICF is thought to index NMDAR-mediated excitatory neurotransmission in the cortex [39, 46] though GABA and other neuromodulators may also contribute to ICF. A **review of TMS studies of cortical excitability** in patients with MDD indicated no significant differences in cortical excitability measures [47]. However, there were cortical inhibitory deficits as measured by intra-cortical inhibition and silent cortical period, both thought to be linked GABA function. Interestingly, Levinson et al. found increased resting motor threshold (RMT) in TRD compared with unmedicated MDD patients, medicated/ euthymic MDD patients, and healthy subjects [48]. While chronic (30 days) administration of paroxetine in healthy subjects induced a significant increase in ICF, single intravenous administration of serotonergic antidepressants, citalopram and clomipramine reduced motor cortical excitability in TRD patients [49]. These findings raise the intriguing question whether any reductions in cortical excitability in TRD patients could be ameliorated by Ketamine's ability to increase cortical excitability.

### Auditory steady state response (ASSR) and Gamma band oscillations

Gamma band oscillations (30-80 Hz) are thought to play a critical role sensory and cognitive processing, and in the pathophysiology of a number of neuropsychiatric disorders. The auditory steady state response (ASSR) is a widely used non-invasive electroencephalography (EEG) technique to study cortical gamma oscillations in auditory cortex. The ASSR evoked power is thought to be regulated by interaction of NMDA receptor and parvalbumin (PV) gamma aminobutyric acid (GABA) inhibitory interneuron activity on sensory cortical pyramidal [50, 51]. Ketamine and NMDA antagonists dose-dependently increases ASSR power and gamma oscillations [52, 53] and causes increased cortical excitability likely by shifting excitatory/inhibitory balance at the circuit level [25, 54, 55]. Further, there has been recent initial validations of ASSR at 40 Hz frequency as a potential marker of NMDA activity [56]. Only one study looking at ASSR using MEG study reported no change in MDD patients compared to healthy subjects but significantly larger ASSR power if compared with BD patients [57]

The main objectives of this project are to investigate the antidepressant effect of low dose Ketamine on cortical excitability and plasticity in the Dorsal Lateral Prefrontal Cortex (DLPFC) of patients with TRD using TMS-EEG. We had previously collected cortical excitability data from 4 health volunteers. We first determined resting motor thresholds (RMT) as the lowest stimulator output intensity which elicited an MEP greater than 50  $\mu\text{V}$  in at least 5 out of 10 trials. RMTs were found to be comparable across participants ( $M=53.8$ ,  $SE=5.0$ ), purple) and commensurate with previous investigations in the literature. Bipolar EMG recordings of the APB muscle during TMS at 100% RMT demonstrated a mean peak to peak amplitude of 569  $\mu\text{V}$ . To measure ICF, an initial conditioning pulse applied at 80% of RMT was followed by a test pulse at 100% RMT at an inter-stimulus interval of 10 ms. MEP responses at this latency resulted in an increased mean peak to peak MEP amplitude of 1381  $\mu\text{V}$ - a 233% increase over the single pulse response. Our assessment of motor cortex excitability was determined to be robust and reliable with a total data collection time of less than four minutes and minimal data processing. Thus, our TMS indices are a straightforward and ideal index of Ketamine-induced cortical excitability changes.

Exploratory Aim: To investigate Ketamine's acute excitatory glutamatergic effect on cortex as indexed by the ASSR. The first goal of the study is to deploy auditory steady state response (ASSR) and gamma band oscillations as a marker of Ketamine's early excitatory effect on cortex. We previously studied the feasibility of quantifying the effect of pharmacological manipulations on cortical ASSR power. We studied the effect of amphetamine, which increases synaptic dopamine neurotransmission. Twelve healthy subjects (mean age  $30.3 \pm 10$ , M:F 7:5) took part in a double-blind, cross-over, placebo-controlled study of single-dose amphetamine (0.5 mg/kg) administration. Subjects performed the ASSR task, involving auditory click trains consisting of binaural presentations of 1 ms duration tones repetition frequencies of 40 Hz, 30 Hz, or 20 Hz. To ensure attention to stimuli, click trains were presented as an oddball paradigm. Electroencephalographic (EEG) data during task performance were collected on a 128 channel Geodesic Sensor Net. Off-line de-noising and averaging will be performed with EEGLAB (62), and wavelet analyses with Brain Vision Analyzer. The average evoked gamma power was derived for the 40 Hz stimuli over the interval 225–525 ms after stimulus onset. Amphetamine showed decreases in gamma power specifically to the 40 Hz stimuli ( $t=2.3$ ,  $p<.05$ ,  $d_z=0.66$ ). Time frequency plots of gamma power after amphetamine for 40 Hz stimuli demonstrated amphetamine induced decreased gamma power. ASSR-EEG paradigm may be well-suited to tracking Ketamine induced modulations in gamma oscillations as implemented in this project

## **Study Design and Procedure**

We will employ an open-label study in which the infusion session, the enrolled TRD patients will receive low dose Ketamine (0.5 mg/kg) over 40 minutes as previous studies [58].

The overall study design is described in Figure1 above.

**Ketamine infusion:** We will use slow infusions of ketamine over a time period of 40 minutes. Study drug will be provided in syringes, containing clear solutions of 1 ml of (0.5mg/kg) ketamine. The dosage will be calculated using the patient's weight in kilograms. For dosing purposes, 0.5-0.9 round up to the next dose and from .01-0.49, we will round down to the lower dose. An ACLS psychiatrist ([name]) will monitor the patient at HCPC. The administration of ketamine will be initiated by the anesthesiologist. The anesthesiologist will be present during the ketamine administration (40 minutes) and post-procedure (until patient is awake and anesthesiologist deems patient is clinically stable). The infusions will be conducted in our hospital during the mornings in a room set specially for this study. During the infusion, patients will be asked constantly about "how they feel" and will receive constant attendance from a psychiatric nurse and the attending ACLS- trained psychiatrist. ECG and pulse oximetry monitoring will be maintained throughout the infusions to check for hemodynamic changes.

After completion of each 40 minute infusion, patients will rest for 2-4 hours under observation of the clinical nurse before being discharged to a responsible adult who will accompany the patient home after completing study tasks. Standard blood sample measurements may occur before the infusion day. All participants will undergo urine drug tests before each infusion. During the course of infusions, patients will receive treatment-as-usual from their primary psychiatrists as would be the case in a traditional therapeutic setting. There will be no changes in medication regimen throughout the 2-week trial. Participants will be provided with a contact card directing them to the nearest ER/physician in case of emergency. We will make it clear to the patient that all of the study procedures are optional at patients' and the PIs discretion.

**Cortical Excitability-TMS procedure:** TMS-EEG will be performed at 4 hours, 24 hours and 7 days after the infusion. Patients will be seated in an armchair with elbow semi-flexed; the forearm pronated and fully relaxed. Participants will be given ear plugs for comfort and noise safety. A MagVenture MagPro X100 transcranial magnetic stimulator system with a figure-of-eight coil (diameter=70 mm for each loop) will be placed tangentially over the scalp overlying the primary motor cortex and DLPFC. The stimulator is paired with Localite neuronavigation system which allows precisely localized stimulus application and its integration also allows

external control of the MagPro system. EMG readings may be obtained from the APB muscle. TMS stimulation will be applied to the corresponding region of the contralateral primary motor cortex. The optimal coil position will be determined by moving the coil in 1-cm increments over the motor cortical area while delivering magnetic pulses and by observing maximal contraction of the contralateral APB. The procedure may be repeated for the opposite hemisphere. The main purpose of this study is to examine the cortical excitability measures after Ketamine. Resting motor threshold (RMT) is defined as the stimulation intensity eliciting an MEP greater than 0.5 mV in 5 of 10 trials with a relaxed APB. Intra-cortical facilitation (ICF) is defined as subthreshold conditioning stimulus set at 80% of resting MT calibrated to produce an average MEP of 0.5- to 1.5-mV peak-to-peak amplitude in the contralateral APB. A suprathreshold test stimulus follows conditioning stimulus between 10-20 milliseconds (ms) (55). Conditioning stimuli may be delivered to left Dorsolateral Prefrontal Cortex (DLPFC) or Brodmann Area 6 or Motor cortex prior to the test stimulus in 1 of 3 random inter-stimulus intervals 10 ms (ICF-10), 15 ms (ICF-15), and 20 ms (ICF-20) for ICF measures. The sequence of administration will be counterbalanced to reduce order effects. For ICF, the change in test stimulus MEP amplitude of each inter-stimulus interval was expressed as a percentage of the mean unconditioned MEP amplitude (55). TMS will be applied concurrently with EEG recordings. **EEG/EMG Acquisition and Analysis** - EEG sessions will be conducted in a sound-attenuated room lit with a low-level ambient light. EEG Brain Products Brain Amp MRPlus 64 channel system is used to acquire EEG data. EEG signals are recorded with a 64 channel cap at a high sampling rate (500 Hz) from the entire scalp, with signals amplified by a shielded, MR-compatible amplifier. The software, Brain Vision Recorder, will be used to coordinate EEG recordings with EPrime. Continuous data will be filtered off-line with a .2- to 100-Hz bandpass filter with a 60-Hz ideal notch filter. ASSR Epochs are defined as -500 to 1000 ms relative to stimulus onset adjusted to a -350 to -150-ms prestimulus baseline. Ocular and ECG artifacts will be removed with ICA-based detection and correction methods (EEGLab); [59]. Data will be re-referenced to average reference. EMG data will be obtained using the Brain Amp ExG amplifier which allows for up to 8 simultaneous bipolar recordings at a 5-kHz sampling rate via the same software as EEG data. MEP epochs will be defined as -200 to 300 relative to stimulation. ICF trials will be time adjusted to align the second pulse with single pulse trials, and MEP amplitudes will be determined as the peak to be difference identified between 10 and 50 ms post-TMS pulse. Software and hardware for the analysis of EEG/EMG data, include state-of-the-art analytic and statistical packages (e.g. EEGLab, Brainstorm, Matlab, and SPSS).

**OPTIONAL: ASSR/EEG paradigm:** Task - Patients will wear ER-3A insert earphones (Etymotic Research, Elks Grove, IL, USA) for auditory stimuli and will be seated ~80 cm from an LCD computer monitor used to present visual stimuli. All stimuli are presented using E-Prime software (Psychological Software Tools, Pittsburgh, PA, USA). Click trains of 500-ms duration will be presented binaurally at  $65 \pm 5$  dB. The click train repetition frequencies will be 40 Hz and presented in the context of an auditory oddball paradigm to ensure participant attention to the stimuli. Standard stimuli will be click trains with individual clicks being 1-kHz carrier frequency whereas Oddball stimuli will be click trains with clicks of 2-kHz carrier frequency. During click train presentation and for 200 ms after click train cessation, the screen remained blank (black). Participants will be then prompted by the appearance of a central fixation cross to respond by button press with either their left index finger for Standard stimuli (110 trials per block) or their right index finger for Oddball stimuli (10 trials per block). Behavioral analyses will be conducted to confirm attention to task but only correct Standard trials will be submitted for EEG analyses.

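### Applied as written, the 60-Hz ideal notch would smear each TMS pulse into time-locked ringing in the TMS-EEG, because no step removes the pulse before filtering

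*Combined protocol and SAP*

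**What the plan says.** The Objectives section states the aim as studying "cortical excitability and plasticity in the Dorsal Lateral Prefrontal Cortex (DLPFC) of patients with TRD using TMS-EEG". Under Study Design and Procedure, "TMS-EEG will be performed at 4 hours, 24 hours and 7 days after the infusion", and the Summary adds a baseline session. The pulses fall inside the EEG record: "TMS will be applied concurrently with EEG recordings".

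The sentences that follow, under EEG/EMG Acquisition and Analysis, hold the only EEG processing rule in the document. EEG is sampled at 500 Hz. Then: "Continuous data will be filtered off-line with a .2- to 100-Hz bandpass filter with a 60-Hz ideal notch filter". An epoch and baseline are given for the ASSR. Then "Ocular and ECG artifacts will be removed with ICA-based detection and correction methods", and the data are re-referenced to the average. Notch width and filter order are not stated. Nothing cuts, blanks or interpolates the TMS pulse, and no epoch, baseline window or response variable is defined for TMS-EEG. The Statistics section adds no EEG processing.

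EMG, from which the motor measures are derived, is recorded on a separate amplifier at 5 kHz.

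**The concern.** An ideal notch sets a narrow frequency band exactly to zero. In the time domain it subtracts a slowly fading 60-Hz oscillation, on both sides of any sharp event. That does little harm to ordinary background EEG. A TMS pulse, however, can leave a transient far larger than the brain response, and filtering the continuous record while the transient is still in it spreads part of it over hundreds of milliseconds. The result looks like an evoked oscillation at 60 Hz, inside the 30-80 Hz range that the protocol calls gamma. It also enters any pre-pulse baseline.

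At stake is whether the EEG response to TMS, which the main objectives rely on, can be read as a cortical response at all.

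**Working it through.** The documents give no figure to reproduce, so the check asks what the stated rule does to a pulse.

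**Inputs from the documents.** Sampling at 500 Hz; band-pass 0.2-100 Hz; ideal notch at 60 Hz; filters applied to continuous data; pulses present in those data.

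**Assumed inputs.** Artefact size (1 mV for reference), artefact shape, notch width B (1, 2 or 4 Hz), and a second-order Butterworth band-pass run forwards and backwards.

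**Formula.** The component that an ideal notch of width B removes from an isolated transient is approximately

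r(t) = 2 · B · g · |X(60)| · sinc(B·t) · cos(2π·60·t + phase), with sinc(u) = sin(πu)/(πu).

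Here |X(60)| is the artefact's spectrum at 60 Hz and g is the band-pass gain there (0.92 for the assumed filter). The formula is symmetric in time, so the ringing precedes the pulse as well as following it.

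**Numbers for a 1 mV artefact with 4-ms exponential decay.** At 500 Hz, 60 Hz is 2π·60/500 = 0.754 rad per sample, and the decay per sample is exp(-2/4) = 0.607. So |X(60)| = 1000 × 0.002 / |1 - 0.607·exp(-0.754i)| = 2/0.695 = 2.88 µV·s.

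| Notch width | 2·B·g·\|X(60)\| | × sinc(B × 0.1 s) | Ringing at 100 ms | Plus band-pass offset of about 2.2 µV | Simulated peak, 100-300 ms |
|---|---|---|---|---|---|
| 1 Hz | 5.3 µV | 0.984 | 5.2 µV | 7.4 µV | about 7 µV |
| 2 Hz | 10.6 µV | 0.935 | 9.9 µV | 12.1 µV | about 12 µV |
| 4 Hz | 21.2 µV | 0.757 | 16.0 µV | 18.2 µV | about 18 µV |

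The simulated column is the average over 100 jittered pulses. It matches the isolated-pulse calculation, which confirms that averaging does not remove the ringing. Distortion of similar size appears from -300 to -30 ms.

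**Other shapes at 1 mV.** A single-sample artefact gives 4.4-12 µV at 100-300 ms and a brief biphasic one 2.6-7.5 µV, over the same notch widths.

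**Second check, flat-topped artefacts, peak to peak at 30-300 ms.** For 1 mV lasting 6 ms and a 2-Hz notch, |X(60)| = 2 × (1 + 2·cos 0.754) = 4.92 µV·s. Peak to peak is then 2 × (2 × 2 × 0.92 × 4.92) = 36 µV, and simulation gives 35.5 µV. At 0.3 mV it is 10.7 µV and at 5 mV 178 µV, so it scales linearly. Over all 1 mV flat-topped shapes tried (one or two phases of 2-10 ms, notch 0.1-10 Hz) the range is 0.5 to 324 µV. The width of that range shows how little the documents fix.

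**Which filter is responsible.** The band-pass alone leaves 0-2.2 µV for the first three shapes. For the flat-topped shapes it leaves 0.25 µV or less, except one at 5.6 µV. The notch is the main source.

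**After the remedy.** Cutting and interpolating -4 to +24 ms before the same filters, for the 4-ms-decay artefact and a 2-Hz notch, leaves 0.04 µV at 100-300 ms and about 0.55 µV at most from 30 ms, against 12 µV without it.

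**The case against.** The strongest reply is that the filter sentence was written for the ASSR, since the next sentence defines ASSR epochs. That is plausible. But the sentence stands under a general EEG/EMG heading, directly after the statement that TMS runs during the EEG, and no other chain exists. If it is meant for the ASSR only, the TMS-EEG in the main objectives has no processing rule. The same passage needs amending on either reading. An unwritten pulse-removal step cannot be excluded either, since the finding rests partly on silence.

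Several other limits stand:

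- The magnitudes rest on assumed artefact size, shape and notch width.
- RMT, MEP and ICF, which the protocol uses as its cortical excitability measures, come from the EMG channel. The plan does not clearly apply this filter to EMG. The Power Analysis rests on ASSR and RMT, not on a TMS-evoked EEG response.
- No TMS-evoked gamma outcome is defined. The gamma measure described is the auditory 40-Hz response.
- Filtering is off-line, so it can be redone if the raw recordings are kept. The neurophysiological assessment is also headed as optional.

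A reader might go further and infer a spurious ketamine effect: the background says ketamine lowers motor threshold, so stimulator output, and with it the artefact, would be smaller after infusion in this uncontrolled comparison. The documents do not support that chain. They do not say the threshold is still lowered at 4 hours, 24 hours or 7 days, and they do not tie DLPFC stimulation intensity to threshold for TMS-EEG. The figures above are also distortion within one session, not a change between sessions. If output fell by an assumed 5-10% with the setup otherwise constant, the 12 µV case would change by 12 × 0.05 = 0.6 to 12 × 0.10 = 1.2 µV.

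**Conclusion.** The point holds as a defect in the stated processing rule for TMS-EEG. Followed literally, the ideal notch writes pulse-locked 60-Hz ringing into the response and its baseline. Per assumed 1 mV of artefact and for notches of 1-4 Hz, the distortion at 100-300 ms is about 7-18 µV for a 4-ms decay and about 3-12 µV for briefer shapes. About 2 µV of the first range comes from the band-pass. The true size could be much smaller or larger, because the documents fix neither artefact amplitude nor notch width.

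Damage to the EMG measures is not shown. A drug-related before/after bias is possible but not established. Because the step is off-line and reversible from raw data, this should be fixed before analysis; it does not make the recordings unusable.

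**What to change.** In EEG/EMG Acquisition and Analysis, give TMS-EEG its own off-line chain:

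1. Cut and interpolate a stated window around each pulse before any filter is applied (for example -4 to +24 ms, the window checked above).
2. Drop the ideal notch for TMS-EEG, or replace it with line-noise regression, and filter only after the pulse has been removed.
3. Keep the unfiltered raw recordings.
4. Limit the present filter sentence to ASSR recordings made without TMS. The Summary lists ASSR and TMS-EEG separately, while the section Neurophysiological assessment (Optional) says TMS and EEG are concurrent, so the amended text should say which recordings contain pulses.

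The cost is a few lines of protocol and analysis code, and the loss of roughly the first 20-25 ms of EEG after each pulse. No visit or patient is added. Recording EEG at 5 kHz is not needed for this fix, since pulse removal works at 500 Hz in the check above. A separate statement about EMG filtering is not needed either.
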